10.2 Statistical Hypotheses

- a. First Hypotheses

The Null Hypothesis: There are no differences between patients receiving an active treatment (N-PPDS) vs. a placebo (p-PPDS) in controlling post-operative ocular pain associated with cataract surgery

Alternative Hypothesis: There are differences between patients receiving an active treatment (N-PPDS) vs. a placebo (p-PPDS) in controlling post-operative ocular pain associated with cataract surgery

b. Secondary Hypotheses

The Null Hypothesis: There are no differences between patients receiving an active treatment (N-PPDS) vs. a placebo (p-PPDS) in controlling post-operative ocular inflammation associated with cataract surgery

Alternative Hypothesis: There are no differences between patients receiving an active treatment (N-PPDS) vs. a placebo (p-PPDS) in controlling post-operative ocular inflammation associated with cataract surgery.

10.3 Analysis Datasets

Data will be pooled from all study centers for data analysis, unless otherwise specified. Study dataset will be generated (keypunched) from original (white) case report forms that have been reviewed and collected from clinical sites. Dataset will contain rows of individual subject data; each row will be clear labeled with the study subject randomized study number and initials. Each column of the dataset will contain a specific parameter for all study subjects. Unmasking the treatment code will not occur until the dataset has been keypunched, data has been verified, and codes or classifications have been assigned.

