10.4.2 Analysis of the Primary Efficacy Endpoint(s)

The primary efficacy variable will be the severity of ocular pain report at visit 4, 5, 6 and 7 (post-op days 1, 3, 7 and 14). For analyses using the intent-to-treat (ITT) data set, all data from all subjects with at least one post-operative follow-up pain evaluation will be included. For the per protocol (PP) analyses dataset, data from subjects or visits with significant protocol deviations will be excluded.

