10.4.3 Analysis of the Secondary Endpoint(s)

The secondary efficacy variable will be the severity of ocular inflammation (anterior chamber cells and flare) report at visit 4, 5, 6 and 7 (post-op days 3, 7 and 14). For analyses using the intent-to-treat (ITT) data set, all data from all subjects with at least one post-operative follow-up inflammation evaluation will be included. For the per protocol (PP) analyses dataset, data from subjects or visits with significant protocol deviations will be excluded.

Efficacy analysis of primary and secondary endpoints will be based on observed data only. In the case of a significant amount of missing data, Last Observation Carried Forward may be used for sensitivity analysis.

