10.4.4 Safety Analyses

All study subjects who are exposed or deemed exposed to study medication will be evaluable for safety analysis. A subject is deemed exposed to study medication if they discontinue the study prior to surgery visit and were implanted with a masked PPDS.

The safety endpoints in this study are adverse events, visual acuity, slit-lamp parameters (Lid, conjunctiva, cornea), fundus findings, and use of rescue medication. Safety variables will be summarized using descriptive statistics.

The type, severity, duration and frequency of reported adverse events will be tabulated for each treatment group, by visit. Adverse events will also be summarized for events and a comparison of the proportion of study patients reporting adverse events between groups will be made using a chi-square test. Additionally, any adverse event experienced by a subject after signing informed consent and before exposure will be presented separately in the safety analysis.

Adverse events will be coded using the Medical Dictionary for Regulatory Activities (MedDRA). Treatment emergent AEs (those occurring after insertion of a study PPDS) will be summarized descriptively: The number and percentage of study subjects who experienced an AE and the total number of AEs will be summarized by system organ class and preferred term. Associated AEs, defined as AEs suspected to be treatment related by the investigator, SAEs and serious associated AEs will also be summarized, if necessary. Summaries of each type of event will be prepared by severity and for all severities combined.

Concomitant medication recorded and used during the study will be coded using the World Health Organization Drug Dictionary and listed by subject. Ocular concomitant medications will be identified by each eye in the listing.

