10.4.9 Tabulation of Individual Response Data

Reports of ocular pain will be tabulated by treatment group, by number of patients reporting ocular pain as either “No Pain” or “Pain” (trace to severe) at each follow-up visit (Visit 4 through Visit 7).

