10.6.1 Enrollment/ Randomization/Masking Procedures

Randomization will be stratified (or balanced) by study center. Patients will be randomized in a ratio of 2:1, 2 active (N-PPDS) for each placebo (p-PPDS). Treatment assignments for this study have been randomized in blocks of three (each sequential group of three, two lines are active treatment, and one line is placebo treatment), 25 blocks total. Using a random number generator (JMP 10.0 statistical software), each block is assigned three randomized numbers. The dataset is then sorted by ascending order by block, by random number. By ascending order, each line is assigned a subject number (e.g. 101-175). As a subject qualifies for enrollment, they will be sequentially assigned a subject number. The subject numbers designated what treatment group the subject will be assigned.

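### Randomization is stratified by centre, but the efficacy sections state no centre-stratified or centre-adjusted comparison: a minor gap, harmless unless centres differ widely, and cheap to close

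*Combined protocol and SAP*

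**What the plan says.** All references are to the combined protocol and SAP.

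- **Design (10.6.1).** "Randomization will be stratified (or balanced) by study center". Allocation is 2:1, and "Treatment assignments for this study have been randomized in blocks of three", 25 blocks in all. On numbering: "By ascending order, each line is assigned a subject number (e.g. 101-175"), with numbers then given out in sequence as subjects qualify. The synopsis allows up to three sites.
- **Handling of centres (10.3).** "Data will be pooled from all study centers for data analysis, unless otherwise specified".
- **Primary efficacy (10.4.2).** "The primary efficacy variable will be the severity of ocular pain report at visit 4, 5, 6 and 7". The section gives the ITT and per-protocol data sets but no test, model or covariate.
- **Secondary efficacy (10.4.3).** "The secondary efficacy variable will be the severity of ocular inflammation (anterior chamber cells and flare"). It adds observed-data analysis and a possible LOCF sensitivity analysis, again with no test.
- **Pain tabulation (10.4.9).** "Reports of ocular pain will be tabulated by treatment group", as pain or no pain at each follow-up visit. Centre is not mentioned.
- **The only between-group test named in section 10** is for safety (10.4.4): "a comparison of the proportion of study patients reporting adverse events between groups will be made using a chi-square test".

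Section 10.2 nevertheless states hypotheses for pain and inflammation, and 10.4.1 sets a two-sided 5% level. Least-squares means appear in the abbreviation list, but no model in the text uses them.

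**The concern.** When randomization is balanced within centre, differences between centres do not bias the treatment comparison. They do stay in the variance of an unadjusted test, which is therefore too large. The test then rejects too seldom under the null and misses some real effects. A comparison made within centres removes that excess.

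Centres could differ here. Section 7.2.2 leaves open-label medication to each surgeon's custom, and site investigators record the pain and anterior chamber grades. With 25 placebo subjects there is little information to spare, and 10.4.7 uses an unmasked look at the efficacy endpoints to decide whether enrolment goes on.

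**Working it through.** **No planned figure to reproduce.** Section 10.5 makes no sample size calculation. The one piece of arithmetic agrees: 25 blocks × 3 = 75 = 50 + 25.

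**Inputs from the documents.** 50 vs 25 subjects (4.1); two-sided 5% (10.4.1). From 2.1, pain-free on Day 1 is about 80% vs 50%; pain-free on Day 14 is 86% vs 46% in one of two studies; inflammation cleared on Day 14 is 65% vs 32% and 61% vs 24%. These are background rates, not design assumptions.

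**Assumptions.** Three centres receiving 8, 9 and 8 whole blocks, so 16/8, 18/9 and 16/8 active/placebo; a common odds ratio across centres; centre placebo rates as listed.

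**Holding the cited overall rates.** With placebo rate p0k in centre k, the active rate is p1k = OR·qk/(1 + OR·qk), where qk = p0k/(1 − p0k). OR is solved so that (16·p11 + 18·p12 + 16·p13)/50 equals the cited active rate. At 20/50/80%, OR = 5.66 gives active rates of 58.6, 85.0 and 95.8%: (9.38 + 15.30 + 15.33)/50 = 0.80.

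**Tests.** For centre k let ak be active responders, mk all responders, and n1k + n0k = nk.

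- Stratified (CMH, no continuity correction): [Σ(ak − n1k·mk/nk)]² / Σ[n1k·n0k·mk(nk − mk)/(nk²(nk − 1))].
- Unadjusted: the same formula on the single pooled table (Mantel-Haenszel variance). Multiplying by 75/74 gives Pearson. These two give the lower and upper ends of each unadjusted range.

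Power is exact, summed over all 153 × 190 × 153 = 4,447,710 possible outcomes.

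| Overall rates | Placebo rate by centre | OR | CMH power | Unadjusted power | Unadjusted type I error |
|---|---|---|---|---|---|
| 80 vs 50% | 50/50/50 | 4.00 | 75.8 | 75.1–76.8 | 5.0–6.0 |
| 80 vs 50% | 40/50/60 | 4.13 | 76.8 | 75.3–77.0 | 4.7–5.7 |
| 80 vs 50% | 30/50/70 | 4.58 | 79.5 | 76.0–77.8 | 3.8–4.7 |
| 80 vs 50% | 20/50/80 | 5.66 | 83.9 | 77.4–79.4 | 2.5–3.2 |
| 86 vs 46% | 26/46/66 | 8.67 | 96.9 | 96.0–96.4 | 3.9–4.6 |
| 86 vs 46% | 16/46/76 | 11.74 | 98.2 | 96.9–97.3 | 2.6–3.1 |

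From unrounded values, the power forgone for Day 1 pain is −0.3 to 1.5 points at 40/50/60%, 1.6 to 3.4 at 30/50/70% and 4.6 to 6.5 at 20/50/80%. For Day 14 pain it is 0.5 to 0.9 and 0.9 to 1.3. The 6.0% with centres alike is Pearson's own small-sample error rate and not an effect of ignoring centre; CMH is at 4.8% there.

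**Cost of stratifying when centres are alike.**

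- Day 1 pain: 75.8 vs at most 76.8, a cost of up to 1 point.
- Inflammation cleared: 78.2 vs 78.7–80.8 (65 vs 32%) and 87.6 vs 87.9–89.6 (61 vs 24%), a cost of 0.3 to 2.6 points.
- Interim of 27 subjects (nine blocks, 6/3 per centre assumed; 10.4.7 says only at least 25), pain: 37.5 vs 35.6–39.8 at 80 vs 50% and 60.8 vs 58.4–64.4 at 86 vs 46%. That is about 2 to 4 points below Pearson and about 2 above the Mantel-Haenszel-variance version.

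**The case against.** The strongest reply is that no efficacy test is named at all, so no unadjusted analysis is actually planned. The pooling sentence sits under data sets, carries its own exception and forbids no centre term. This stands. The missing test is the wider gap, and centre is one element of filling it. It is still worth stating, because the trial randomizes by centre and nothing in the efficacy sections carries that through.

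The second reply is that wide spreads are unsupported. No between-centre figure is given. Appendices 2 and 3 impose common grading scales, NSAIDs and corticosteroids are prohibited, and 7.2.2 also asks that open-label medication be consistent for all cases. This stands too, and it makes the narrower rows the more credible ones.

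A reader might infer a larger loss by fixing the within-centre odds ratio at 4 while the centres spread. At 20/50/80% that gives 67.2 vs 58.2–60.0, a loss of 7 to 9 points. But the overall active rate is then (8.00 + 14.40 + 15.06)/50 = 74.9%, not the cited 80%, so much of the fall from about 76% is a smaller overall effect. With the cited overall rates held, unadjusted power does not fall as centres diverge; what is lost is the gain available from stratifying.

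A reader might also infer from the number series in 10.6.1 that one list is shared across centres and stratification fails. The series is only an example, the same section says stratified, and 11.3 refers to a site/subject number. The text is unclear but does not show that.

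**Conclusion.** The point holds as a minor one. The stated efficacy analysis does not use the factor by which the trial randomizes. The consequence is conditional and runs towards conservatism: nothing is lost when centres are alike, about 2 to 3 points for Day 1 pain at a 40-point spread in placebo rates, about 5 to 6 at a 60-point spread, and about 1 point or less for Day 14 pain.

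A reader might infer that pooling invalidates the comparison or raises the false-positive rate. The figures do not support that. Nor is any planned power missed, since this is a pilot with none stated.

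The figures rest on three centres of near-equal size, 2:1 allocation within each, a common odds ratio, assumed spreads and the binary pain outcome. Six-level severity scores were not evaluated at fixed overall rates. With one enrolling centre the point is moot.

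**What to change.** In 10.4.2 and 10.4.3, name the efficacy comparison and stratify or adjust it for centre:

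- Cochran-Mantel-Haenszel for pain/no pain and for inflammation response, exact if tables are sparse.
- Van Elteren, or a model with a centre term, for severity scores.
- A rule, fixed before any unmasking, for combining very small centres, because a centre with data in only one arm adds nothing to a stratified test.
- The unadjusted result reported as supportive, and a statement of whether the same comparison applies at the interim.

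A cross-reference in 10.3 would supply the exception it allows for. As a clarification only, 10.6.1 could say that whole blocks are assigned to each centre.

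The change is a few sentences, with no added subjects or visits. If centres prove alike, the price is the small loss of power shown above: up to about 1 point for pain, up to about 2.6 points against Pearson for inflammation clearing, and a few points at a small interim.

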10.4 Description of Statistical Methods

10.4.1 General Approach

All statistical tests will be two-sided and interpreted at a 5% significance level. Descriptive statistics (i.e., mean, standard deviation, etc.) will be provided for all continuous variables and frequency distributions will be generated for all categorical variables collected in this study.

10.4.2 Analysis of the Primary Efficacy Endpoint(s)

The primary efficacy variable will be the severity of ocular pain report at visit 4, 5, 6 and 7 (post-op days 1, 3, 7 and 14). For analyses using the intent-to-treat (ITT) data set, all data from all subjects with at least one post-operative follow-up pain evaluation will be included. For the per protocol (PP) analyses dataset, data from subjects or visits with significant protocol deviations will be excluded.

10.4.3 Analysis of the Secondary Endpoint(s)

The secondary efficacy variable will be the severity of ocular inflammation (anterior chamber cells and flare) report at visit 4, 5, 6 and 7 (post-op days 3, 7 and 14). For analyses using the intent-to-treat (ITT) data set, all data from all subjects with at least one post-operative follow-up inflammation evaluation will be included. For the per protocol (PP) analyses dataset, data from subjects or visits with significant protocol deviations will be excluded.

Efficacy analysis of primary and secondary endpoints will be based on observed data only. In the case of a significant amount of missing data, Last Observation Carried Forward may be used for sensitivity analysis.

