7.9 Rescue Medications

During the study some patients, as determined by the investigator, may require additional rescue medications in the study eye due to post-op ocular pain and/or inflammation the patient is experiencing. Rescue treatment will be allowed per pre-specified rescue criteria ([Section 7.9.1](#)); if the rescue criteria are not met, the medications will be considered prohibited medications. Prohibited medications, though discouraged, could be used but would be considered protocol deviations.

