7.9.1 Administration of a Rescue Medication

Following cataract surgery, a rescue treatment with an ocular topical corticosteroid (prednisolone acetate 1% q.i.d.) should be administered in the study eye, at the discretion of the physician, if any of the following rescue criteria apply:

- a. Anterior Chamber Cell grade is 3 (grade 3 = 16-30+ cells) or greater
- b. Anterior Chamber Flare grade is 3 (grade 3 = moderate intensity) or greater
- c. Subject reports moderate to severe ocular pain

A study subject will be followed through Visit 7 (Day 14) or until the study subject's post-op ocular pain and/or inflammation in the study eye has resolved or has become medically stable. The use of a rescue medication during the study will be documented on the Concomitant Medication CRF.

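### No rule covers scores recorded after allowed steroid rescue, so by default a rescued subject who later scores 0 is tabulated as No Pain in the assigned arm

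*Combined protocol and SAP*

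**What the plan says.** All references are to the combined protocol and SAP.

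- **Data used.** For the ITT set, 10.4.2 says "all data from all subjects with at least one post-operative follow-up pain evaluation will be included". The rule in 10.4.3 covers both endpoints: "Efficacy analysis of primary and secondary endpoints will be based on observed data only". It continues: "In the case of a significant amount of missing data, Last Observation Carried Forward may be used for sensitivity analysis".
- **Primary variable.** 10.4.2: "The primary efficacy variable will be the severity of ocular pain report at visit 4, 5, 6 and 7". Section 10.4.9 also tabulates No Pain against Pain (trace or worse) by arm at each visit, with no qualifier for rescue.
- **Rescue.** 7.9: "Rescue treatment will be allowed per pre-specified rescue criteria". Section 7.9.1 names prednisolone acetate 1% q.i.d. for cells of grade 3 or more, flare of grade 3 or more, or moderate to severe pain. The subject is then followed through Day 14, or until resolved or stable. Only steroid given outside the criteria is a prohibited medication and a deviation.
- **Conflicting rule.** 7.7.1 terminates any subject who requires a corticosteroid and has the plug removed, but still follows the subject to Visit 7.
- **Where rescue is analysed.** 10.4.4 lists rescue use as a safety endpoint: "Safety variables will be summarized using descriptive statistics".
- **Exclusions.** In the per-protocol set, "data from subjects or visits with significant protocol deviations will be excluded". Section 10.1 allows discretionary exclusion for major violations. Section 10.6.3 has each subject and visit assessed for evaluability before lock and unmasking.

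**The concern.** The objective in Section 3 is the plug's own effect on post-operative pain and inflammation. A subject who reaches moderate pain or grade 3 cells has failed on the plug in the ordinary sense. If prednisolone then brings the score to 0, the plan's default records a success for the plug at every later visit. Rescue use appears only in a safety table.

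Placebo subjects would probably be rescued more often, so the default would tend to pull the arms together at Days 3, 7 and 14. Day 1 is little affected. The interim continuation look (10.4.7) uses the same endpoints. Section 2.2 chose placebo so that results could be compared with earlier nepafenac studies, and that comparison needs a stated rescue rule.

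**Working it through.** **1. Tracing one subject.** Suppose pain is 1 at Day 1 and 3 at Day 3, prednisolone is started at Day 3, and pain is 0 at Days 7 and 14.

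| Provision | Day 3 | Days 7 and 14 |
|---|---|---|
| 7.9.1 with 10.4.2, 10.4.3, 10.4.9 | Pain | No Pain, assigned arm |
| 7.7.1, later scores used | Pain | No Pain, assigned arm, plug out |
| 7.7.1, later scores not used | Pain | Missing, so dropped |
| LOCF (10.4.3) | – | Could carry the 3 forward, but only if scores are missing; optional, sensitivity only |
| Per-protocol or 10.1 exclusion | – | Removed if judged a violation; criteria-met rescue is not clearly one |
| 10.6.3 assessment | – | Evaluability decided under mask, with no criterion for rescue |

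No row sets a rule that makes Days 7 and 14 failures.

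**2. Size, Pain/No Pain.** The plan has no power figure to reproduce: 10.5 disclaims a sample size calculation and no efficacy test is named. Inputs from the documents are n = 50 and 25, two-sided 5% (10.4.1), and Day 14 pain-free rates of 86% and 84% against 46% and 38% (2.1). Assumptions: the midpoints, 85% and 42%, are the plug-alone rates; f is the share of non-pain-free subjects rescued; s is the share of those who score 0 on steroid (50% to 100%); the test is Fisher's exact.

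Observed rate = p + (1 − p) × f × s. For f = 25% and s = 1: active 0.85 + 0.15 × 0.25 = 0.8875; placebo 0.42 + 0.58 × 0.25 = 0.565; difference 32 points.

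| f, active / placebo | Difference, s = 50% to 100% | Power |
|---|---|---|
| 0 / 0 | 43 | 96% |
| 10% / 10% | 41 to 39 | 94% to 92% |
| 25% / 25% | 38 to 32 | 91% to 84% |
| 10% / 25% | 37 to 30 | 89% to 76% |
| 25% / 10% | 42 to 41 | 96% |
| 50% / 10% | 44 to 45 | 97% to 99% |

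The last two rows show that dilution is likely but not certain. It disappears or reverses if a much larger share of active-arm failures is rescued.

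**3. Termination reading with later scores dropped.** Rate = p / [p + (1 − p)(1 − f)]. With 86% and 46% and f = 50%: 0.86/0.93 = 92.5% and 0.46/0.73 = 63.0%. The difference is 29.5 points, against 40 if rescue counts as failure.

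**4. Severity (0 to 5), Wilcoxon by simulation.** Assumed: rescued subjects are at 3 before rescue; other painful eyes are split equally between 1 and 2 (mean 1.5). If responders go to 0, at f = 10% the mean difference falls from 0.71 to 0.65–0.58 and power from 97% to 96–94%. At f = 25% it falls from 0.81 to 0.65–0.48 and power from 97% to 93–88%. If responders reach only trace, power stays at 97%.

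Part of that loss is built in, because the baseline holds rescued eyes at 3 until Day 14. Suppose instead that at f = 25% they would have settled to 1.5 untreated. The true difference is then (0.58 − 0.15) × 1.5 = 0.645. Observed data give 0.484, 0.645, 0.591 or 0.699 (responders to 0 or to 1, s = 100% or 50%). Carrying the pre-rescue 3 forward gives 0.43 × (0.25 × 3 + 0.75 × 1.5) = 0.806. That is 0.161 too high, in the drug's favour, and never closer than the observed-data values.

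**5. Interim, about 17 and 8 subjects.** The chance of a zero or negative observed difference is 0.0125 at base, 0.0157 to 0.0196 at f = 10%, and 0.0218 to 0.0359 at f = 25%. The effect is small, and the plan sets no threshold.

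**6. Inflammation.** If complete response means cells and flare both 0 (the plan does not define it), midpoints of the quoted 65/61 and 32/24 give 63% and 28%. Power falls from 81% to 77–71% (f = 10%) or 69–55% (f = 25%).

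**7. Cost of counting rescue as failure.** Suppose a share g of would-be pain-free subjects is rescued for inflammation: rate = p(1 − g). For g = 10% in both arms: 76.5% against 37.8%, 39 points, power 88%. For g = 20% in both: 68.0% against 33.6%, 34 points, 79%. For 10% active and 20% placebo: 76.5% against 33.6%, 43 points, 94%.

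**The case against.** The strongest reply has four parts.

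- **Inference from silence.** The sentence in 10.4.3 is a missing-data rule, and no passage says outright that on-steroid scores count as ordinary scores. This stands: the result follows by default, chiefly from the all-data wording of 10.4.2, and only where 7.9.1 rather than 7.7.1 is followed. The contradiction between those two sections is a defect in its own right.
- **Masked review.** Section 10.6.3 offers a visit-level route for deciding on post-rescue visits. It does, but it supplies no criterion, can exclude a visit without making it a failure, and may not protect the interim look.
- **Legitimate estimand.** Using all observed ITT data is a sound treatment-policy analysis, and this is a pilot. True, but the plan does not declare that choice.
- **The remedy has its own bias.** For severity scores this stands, as step 4 shows. For the responder rule, a subject rescued for flare alone becomes a pain failure, so pain could become a composite unless such subjects are shown separately.

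A reader might infer that the trial is biased towards a false positive, or that power is badly damaged. The documents support neither. The likely direction is towards no difference, and no rescue rate is given. Nor do they support replacing post-rescue severity scores with pre-rescue scores as the main analysis.

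**Conclusion.** The gap is real but conditional. Under 7.9.1, a rescued subject who later scores 0 is tabulated as No Pain (or inflammation-free) in the assigned arm. The later responder contrasts then describe plug plus rescue. Under 7.7.1 the use of later scores is unstated. No provision counts the subject as a failure after rescue.

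The size cannot be fixed from the documents. Under the assumed rates, equal rescue of 10% to 25% of failures costs 2 to 11 points of the 43-point pain contrast. Severity results are less sensitive if steroid brings responders only to trace, and the effect on the interim look is small. The illustrations rest on topical-nepafenac rates, assumed rescue and response shares, and tests that the plan does not name. This is a modest but worthwhile correction. It makes clear what is estimated and may not raise power.

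**What to change.** Amend before the interim unmasking in 10.4.7:

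1. In the per-visit responder analyses (No Pain/Pain; complete and partial response), count a subject as a non-responder once a steroid or NSAID is given for ocular pain or inflammation, or after termination for either. Apply this from the visit where the drug is started, otherwise from the next visit. Report the observed-data analysis beside it, and show separately those rescued for inflammation alone.
2. For severity scores, keep observed data. Carry the last pre-rescue score forward only as a labelled sensitivity analysis, stating that it assumes no natural post-operative resolution and can favour the drug.
3. Do not replace subjects given a steroid or NSAID for ocular pain or inflammation. At present, use outside the criteria can lead to discontinuation and replacement (5.5.1.2, 5.5.2.2).
4. Reconcile 7.7.1 with 7.9.1. Which clinical rule is right is for the sponsor to decide.

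The cost is one IRB-approved amendment (7.1) touching 10.4, 5.5.2.2, 7.7.1 and 7.9.1. No new data are needed: the Concomitant Medication CRF already holds start dates and indications (7.6.2), and unscheduled visits already record pain and slit-lamp findings (7.4.7). The downside is lower response rates in both arms and possibly lower power, as in step 7 of the working.
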